### 5.5.2 Key secondary analysis

*Multiple imputation (Molenberghs & Kenward 2007; White, Royston & Wood 2010)*

Alternative to LOCF, additionally as sensitivity analyses a multiple imputation (Molenberghs & Kenward 2007; White, Royston & Wood 2010) is planned:

\* Impute values via MCMC to obtain a monotone missing pattern\*;

```

proc mi data=&data out=gfr_mono n impute=20 seed=579415 NOPRINT
  by tgplc;
  mcmc chain=multiple impute=monotone;
  var v:;
run;

** Impute values via predictive mean matching *;
proc mi data=gfr_mono out=gfr_imp n impute=1 seed=579214 NOPRINT;
  by tgplc _imputation_;
  monotone regpmm;
  var v:;
run;

ods output LSMeans=LSMeans; *** LsMeans+CL for effects ***;
ods output Estimates=gfr_imp; *LsMeans+CL for contrasts;
proc glm data=gfr_imp;
  by _imputation_;
  class tgplc ctr1n;
  model egfr_im = baseline tgplc HCV_class lab_MELD_class / ss3;
  lsmeans tgplc / stderr ;
  estimate "mean difference" tgplc 1 -1;
run;
quit;

*lsmeans;
proc sort data=LSMeans;
  by tgplc;
run;

ods listing close;
ods rtf exclude all;
ods output ParameterEstimates=LSMeanMI;
proc mianalyze data=LSMeans;
  by tgplc;
  modeleffects lsmean;
  stderr stderr;
run;
*lsmean difference;
proc sort data=LSMeanDiff;
  by parameter;
run;

ods output ParameterEstimates=LSMeanDiffMI;
proc mianalyze data=LSMeanDiff;
  by parameter;
  modeleffects estimate;
  stderr stderr;
run;

```

### *Mixed Model for Repeated Measures (MMRM)*

As a further supportive analysis, a Mixed Model for Repeated Measures (MMRM) will be fitted using treatment group, visit (as a categorical time variable) and subject as categorical

variables (Molenberghs & Kenward 2007). Assuming that the time profile is not the same in the two treatment groups, a full visit-by-treatment interaction will be used. Baseline and the baseline-by-time interaction will be included in the model. An unstructured covariance matrix will be used:

```
proc mixed;
  class subject visit treatment;
  model gfr = baseline tgplc HCV_class lab_MELD_class visit
  baseline*visit tgplc*visit / s ddfm=kr;
  repeated time / subject = subject type = un group=treatment;
run;
```

### **Efficacy-related objectives**

For the efficacy related events only the events between Visit 2 (Baseline) and Day 360 are relevant. That means, that all events outside before Baseline and after 360 are excluded from this analysis.

**Death:** All Cases documented on the following pages

- End of treatment
- Study completion

Date of event = Date of Death – Date of Baseline + 1

**Graft loss:** All cases documented on page Graft Loss

Date of event = Date of Graft loss – Date of Baseline + 1

**Acute rejection:** All rejections documented on page Liver Allograft Rejection with final clinical diagnosis “Acute rejection diagnosed by biopsy”, “Acute rejection diagnosed without biopsy” or “Acute and chronic rejection”.

Date of event = Date rejection was first suspected – Date of Baseline + 1

**Treated acute rejection:** All rejections documented on page Liver Allograft Rejection with [final clinical diagnosis “Acute rejection diagnosed by biopsy”, “Acute rejection diagnosed without biopsy” or “Acute and chronic rejection”] and anti-rejection therapy.

Date of event = Date rejection was first suspected – Date of Baseline + 1

**Biopsy proven acute rejection:** All rejections documented on page Liver Allograft Rejection with final clinical diagnosis “Acute rejection diagnosed by biopsy”.

Date of event = Date rejection was first suspected – Date of Baseline + 1

**Treated Biopsy proven acute rejection:** All rejections documented on page Liver Allograft Rejection with final clinical diagnosis “Acute rejection diagnosed by biopsy and anti-rejection therapy”.

Date of event = Date rejection was first suspected – Date of Baseline + 1

For **Kaplan-Meier analysis** the first occurred event will be used. If no event is treated the time will be censored at min (day of visit Month 12, 360). If visit Month was not performed, the last visit until Month 12 will be used.

Day of vist = Visit Date – Date of Baseline + 1

**Adverse of special interest** were defined as followed:

AE of special interest	Identification
HCV (Hepatitis C Virus)	PT „HEPATITIS C“ OR “HEPATITIS C VIRUS TEST POSITIVE” OR “CHRONIC HEPATITIS C” OR “ACUTE HEPATITIS C” OR “HEPATITIS C ANTIBODY” “HEPATITIS C ANTIBODY POSITIVE” “HEPATITIS C CORE ANTIBODY POSITIVE” PT contains “HEPATITIS C RNA” “HEPATITIS C VIRUS TEST” “HEPATITIS C VIRUS TEST POSITIVE”
HCV related fibrosis	PT “HEPATIC FIBROSIS” (Query: HCV related?)
CMV	HLT “CYTOMEGALOVIRAL INFECTIONS”
Proteinuria	SMQ “PROTEINURIA”
New onset diabetes mellitus	PT contains “Diabetes Mellitus” as Adverse event, but no PT containing “Diabetes Mellitus” as medical history
Hepatocellular Carcinoma (HCC)	HLT “HEPATIC NEOPLASMS MALIGNANT” OR “HEPATOBILIARY NEOPLASMS MALIGNANT UNSPECIFIED”
De novo HCC malignancies	HLT “HEPATIC NEOPLASMS MALIGNANT” OR “HEPATOBILIARY NEOPLASMS MALIGNANT UNSPECIFIED” as adverse event, but no HLT “HEPATIC NEOPLASMS MALIGNANT” OR “HEPATOBILIARY NEOPLASMS MALIGNANT UNSPECIFIED” as medical history

**Concomitant therapy of special interest** were defined as followed.

Concomitant therapy of special interest	Identification
Renal replacement therapy	PT „NON-DRUG THERPY: DIALYSIS“ or ATC CODE “B05Z (HEMODIALYTICS AND HEMOFILTRATES”

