#### **6.6.4      Rescue medication**

##### **Treatment for acute rejection episodes**

Treatment for biopsy proven acute rejection will commence at the clinician's discretion or according to the center-specific protocol. An acute rejection episode will be considered to have been treated if a patient has received at least 3 days' treatment with a daily dose of 15mg/kg (max.1000 mg) or more of i.v. methylprednisolone (or equivalent) and/or at least 3 days of antilymphocyte therapy.

Treatment of acute rejection or presumed acute rejection will be recorded on the appropriate CRF page.

The biopsies will be read locally and the severity of acute rejection will be classified using the Rejection Activity Index (RAI) as defined by the World Gastroenterology Consensus Document (Banff, Hepatology 1997). In the event that a rejection episode is not confirmed by biopsy or a biopsy is not done, the clinician will score the severity of that rejection episode on the basis of clinical and functional criteria into severe (hospitalization, death) and non severe (all others).

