**• Acute rejection episodes**

Acute rejection is defined as a clinically suspected acute rejection, whether biopsy-proven or not, which has been treated and confirmed by the investigator according to the response to therapy. Each acute rejection must be recorded on the relevant CRF page with the clinical diagnosis specified, and, if a biopsy was performed, with the histological diagnosis.

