**• Biopsy-proven acute rejection**

Biopsy-proven acute rejection (BPAR) is defined as a clinically suspected acute rejection confirmed by biopsy. For all clinically suspected rejection episodes a graft biopsy is performed at investigator's discretion before or within a 24-hour period from the initiation of anti-rejection therapy. The local pathologist will grade biopsies. The results of the biopsy read by the local pathologist will be listed in the Allograft Biopsy CRF page.

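### The SAP counts treated BPAR without the protocol's criterion for a treated episode and drops the mixed acute-and-chronic code without looking at the biopsy, and its list of changes mentions neither

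*SAP*

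**What the plan says.** **Protocol 6.6.4 (Rescue medication)** leaves treatment of biopsy-proven rejection to the clinician's "discretion or according to the center-specific protocol". It then states a counting criterion: "An acute rejection episode will be considered to have been treated if a patient has received at least 3 days" of intravenous steroid at or above a stated daily dose (or equivalent), and/or antilymphocyte therapy for the same minimum time. It adds: "Treatment of acute rejection or presumed acute rejection will be recorded on the appropriate CRF page".

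**Protocol 7.5 (Efficacy)** describes acute rejection as a clinically suspected episode, biopsied or not, "which has been treated and confirmed by the investigator according to the response to therapy". No minimum course appears there. Each episode goes on the CRF with its clinical diagnosis and, "if a biopsy was performed, with the histological diagnosis". The same section states: "Biopsy-proven acute rejection (BPAR) is defined as a clinically suspected acute rejection confirmed by biopsy". Results read by the local pathologist go on the Allograft Biopsy CRF page.

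**SAP 5.5.2 (Efficacy-related objectives)** builds each rejection endpoint from a diagnosis code on the rejection page. The BPAR rule reads "All rejections documented on page Liver Allograft Rejection with final clinical diagnosis" followed by the single biopsy-diagnosed code. The treated BPAR rule uses the entry "Acute rejection diagnosed by biopsy and anti-rejection therapy". The rules for acute rejection and treated acute rejection also admit the mixed acute-and-chronic code; the two BPAR rules do not.

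**SAP Section 4** lists four statistical changes from the protocol: HCV fibrosis progression, proteinuria, CMV infection and the treatment-emergent definition. Rejection is not among them.

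**The concern.** The key secondary endpoint is treated BPAR, graft loss or death. It is the main readout of whether a reduced-tacrolimus regimen still protects the graft. The protocol says what makes an episode count as treated, but the SAP derivation that produces the events does not use or cite it. Because treatment is left to the clinician or center, courses below the minimum are possible, and a literal reading of the SAP would count them.

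Separately, the SAP decides BPAR by diagnosis code alone. An episode coded as both acute and chronic rejection is excluded even if its biopsy confirmed the acute component.

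With nothing declared in Section 4, a reader would assume that the reported composite is the protocol's endpoint.

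**Working it through.** **1. Definitions side by side**

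| Element | Protocol | SAP 5.5.2 |
|---|---|---|
| Treated | 6.6.4: minimum duration, with a minimum daily dose for the steroid route, or antilymphocyte therapy. 7.5: treated, no minimum | Anti-rejection therapy, no minimum, no cross-reference |
| BPAR | 7.5: clinical suspicion confirmed by biopsy | One diagnosis code; biopsy page not consulted |
| Mixed acute-and-chronic code | Not mentioned | In acute rejection and treated acute rejection; out of BPAR and treated BPAR |
| Declared in SAP Section 4 | n/a | Neither point |

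One reading is assumed. As printed, the quotation marks in the treated BPAR rule enclose both the diagnosis and the therapy. I read the therapy as a separate condition, as in the SAP's bracketed rule for treated acute rejection. SAP 2.4 and 2.5, which describe the key secondary and secondary analyses, do not supply the missing criterion.

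**2. Direction of each difference**

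- Dropping the minimum can add events or leave the count unchanged.
- Excluding the mixed code can remove events or leave the count unchanged. It removes a true BPAR only where a biopsy confirmed acute rejection; otherwise the exclusion agrees with Protocol 7.5.
- The two act in opposite directions, so the net sign is unknown.

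**3. Reach.** SAP 2.5.1 lists 9 efficacy endpoints.

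- Using the treated rule: treated acute rejection, treated BPAR and the two composites containing treated BPAR = 4.
- Using the BPAR diagnosis rule: BPAR, treated BPAR and the same two composites = 4.
- Using both: treated BPAR and the two composites = 3.
- Using at least one: 4 + 4 − 3 = 5.

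**4. Scale.** The documents give no rejection rate, no count of courses below the minimum and no count of mixed-code episodes, so the effect cannot be calculated. The plan also has no figure for this endpoint to reproduce: SAP Section 3 says that power for secondary variables was not investigated. What can be given is the weight of one patient:

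- Planned arm size 165 (Protocol 10.7), no censoring: 1/165 = 0.0061, or 0.61 percentage points of Month 12 incidence.
- On the planned Kaplan-Meier scale with the protocol's 20% drop-out rate, I simulated 2,000 arms at each of three incidences. Assumptions: uniform event and drop-out times; composite incidence 5%, 10% or 20%. One patient changed from no event to event moved the Month 12 estimate by 0.66 to 0.67 points on average, with central 95% ranges lying within 0.50 to 0.77.

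This is what any single event is worth in that arm, not an estimate of misclassification. The difference between arms moves only if the net number reclassified differs between them.

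**The case against.** The best defence is inheritance. The SAP introduction says that it implements the analysis planned in the protocol. SAP 5.5.2 sets no competing threshold and does not say that any course counts, so it could be read as taking the 6.6.4 criterion for granted, with nothing to declare. That reading is possible. It is not stated, however, and 5.5.2 is where the SAP spells out event derivation code by code. The CRF page or the VAP may settle the matter, but neither is in the documents. Where the documents describe the VAP's content, it concerns protocol deviations and analysis-set exclusions, not event definitions.

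Second, the protocol is not uniform. Its criterion sits under rescue medication, while 7.5 asks only that an episode was treated. This stands, and it means that both documents need aligning. Still, 6.6.4 is the only statement of when an episode counts as treated, and the protocol lists BPAR and treated BPAR separately, so the distinction has to carry meaning.

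Third, the mixed-code problem is conditional on biopsy confirmation, and nothing shows that a course below the minimum occurred. Both limits stand.

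Fourth, the plan contains mitigation. BPAR regardless of treatment is reported and, under the SAP's own code, is an upper bound for treated BPAR at any treatment threshold. Acute rejection and treated acute rejection are reported with the mixed code included. A reader can therefore partly bound the effect for components. The composite is not rerun, and the component tables cannot show which treated episodes met the criterion.

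A reader might go further and infer that open-label clinicians inflated the count, that the exclusion of the mixed code is an outright error, or that the composite is biased toward one arm. The documents support none of these: they contain no episode-level data, and the label does not reveal the biopsy result.

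**Conclusion.** The point holds in limited form. Followed literally, SAP 5.5.2 can count episodes that Protocol 6.6.4 would not call treated, and can omit biopsy-confirmed episodes that Protocol 7.5 would call BPAR. Neither possibility is declared.

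This rests on two conditions: that the unseen CRF or VAP does not already apply the protocol criterion, and, for the mixed code, that at least one such episode had acute rejection confirmed by biopsy. Size and net direction are unknown.

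The consequence is confined to exploratory, unpowered endpoints. The confirmatory eGFR test does not use these events. Correction is worthwhile because the composite is the plan's only key secondary endpoint, but the issue does not threaten the trial's main conclusion.

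**What to change.** Reconcile Protocol 6.6.4, Protocol 7.5 and SAP 5.5.2 so that one event-counting rule defines treated. Either apply the protocol's existing criterion to the recorded anti-rejection therapy, or declare the rule without a minimum as a change in SAP Section 4.

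State in SAP 5.5.2 one explicit biopsy-confirmation rule based on the Allograft Biopsy CRF page. Apply it both to the biopsy-diagnosed code, which is now accepted on its label alone, and to the mixed acute-and-chronic code. Alternatively, declare the exclusion of the mixed code in Section 4. Rerunning the composite under the other rule is an optional sensitivity analysis.

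The cost is SAP text and some programming. The protocol already has rejection treatment, histological diagnosis and biopsy results recorded. Whether dose, route and dates are complete cannot be seen, so episodes with incomplete therapy or biopsy records would need review at the data review meeting. All of this concerns how events are counted, not how patients are treated.

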**• Graft loss**

The allograft will be presumed to be lost if a patient has a liver retransplant or dies due to liver failure.

The reason for graft loss will be recorded on the Graft Loss CRF page. If graft loss occurs after the patient has discontinued study medication prematurely, the graft loss will be entered on the Study Completion and Graft Loss CRF page. Graft loss is considered a Serious Adverse Event and must be reported.

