### **2.4.2 Statistical hypothesis, model, and method of analysis**

The incidence of the composite of treated biopsy proven acute rejection (BPAR), graft loss or death until Month 12 was estimated using the Kaplan-Meier method.

The number of events as well as the number of censored observations will be presented. Kaplan-Meier estimates will be presented by quarter up to Month 12. Percentiles (25%, median, 75%) of the event time distribution will be presented together with their two-sided 95% confidence interval. The two groups were compared using the log-rank test. Kaplan-Meier curve was displayed graphically.

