### **2.4.3 Handling of missing values/censoring/discontinuations**

If no event occurred until Month 12 or End of Study the observation period will be censored at Month 12 (day 360 or at end of study)

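### The Kaplan-Meier rule counts events up to Day 360 but, when Month 12 is missed, censors event-free patients at their last visit, so follow-up depends on outcome

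*SAP*

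**What the plan says.** SAP 5.5.2, under Efficacy-related objectives, sets the event window: "For the efficacy related events only the events between Visit 2 (Baseline) and Day 360 are relevant". Deaths are taken from the End of treatment and Study completion pages, and graft losses and rejections from their own pages. Nothing requires the event to precede the patient's last visit.

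The same section then sets the censoring time: "If no event is treated the time will be censored at min (day of visit Month 12, 360". The wording is garbled but presumably means that no event occurred. For patients without that visit it adds: "If visit Month was not performed, the last visit until Month 12 will be used".

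SAP 2.4.3, on the key secondary endpoint, says "the observation period will be censored at Month 12 (day 360 or at end of study". It does not say which alternative applies, and it gives no date definition for end of study.

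SAP 2.4.2 states the comparison: "The two groups were compared using the log-rank test".

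Protocol 7.5 provides for capture of graft loss after study drug has been stopped: "the graft loss will be entered on the Study Completion and Graft Loss CRF page". Protocol section 7 (Visit 9a and Visit 9) also has rejection and biopsy information collected for patients who stop study drug early.

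**The concern.** Kaplan-Meier estimates and the log-rank test assume that the time a patient is observed does not depend on whether the event will happen. The 5.5.2 rule breaks this for patients without a Month 12 visit.

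Take two hypothetical patients who stop study drug, attend Visit 9a on Day 30 and miss Visit 9. One loses the graft on Day 200, and this is entered on the Graft Loss page: an event, with 200 days at risk. The other is documented alive with a functioning graft on Day 300 and is censored on Day 30. Information on later events is kept, and information on later event-free time is thrown away.

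The endpoint affected shows whether tacrolimus minimisation costs rejections, grafts or lives. An avoidable upward shift in its rates, possibly unequal between arms, would blur that reading.

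**Working it through.** **Figures in the plan.** The documents give no event rate, event count or power for these endpoints (Protocol 10.8). The only design figure concerns eGFR: 105/(1 − 0.2)² = 164.1 per group, against 165 stated. It has no bearing here beyond supplying the arm size. Event rates and missed-visit rates below are therefore assumptions.

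**Set-up.** Let S(t) be the true event-free proportion, m the share of patients who lack Month 12 regardless of outcome, p the share of those already past their last visit in a given interval, w = m·p, f(t) the event density, and q the share of events after the last visit that reach the CRF. Under 5.5.2 a patient past the last visit stays in the risk set only if a captured event is still to come. The hazard that Kaplan-Meier sees is

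f(t)·[1 − w(1 − q)] / {S(t)(1 − w) + w·q·[S(t) − S(360)]}.

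Integrated over an interval from a to b, this gives the survival factor

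[S(b) − c] / [S(a) − c], with c = w·q·S(360) / [1 − w(1 − q)].

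**True rate 10%, m = 20%, q = 1.** The hazard is constant, so S(t) = 0.9^(t/360). Last visits fall equally on Days 30, 90, 180 and 270.

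| Interval (days) | S(a) | S(b) | w | c | Factor |
|---|---|---|---|---|---|
| 0–30 | 1.0000 | 0.9913 | 0 | 0 | 0.99126 |
| 30–90 | 0.9913 | 0.9740 | 0.05 | 0.045 | 0.98177 |
| 90–180 | 0.9740 | 0.9487 | 0.10 | 0.090 | 0.97136 |
| 180–270 | 0.9487 | 0.9240 | 0.15 | 0.135 | 0.96969 |
| 270–360 | 0.9240 | 0.9000 | 0.20 | 0.180 | 0.96771 |

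The product is 0.8871, so the estimated rate is 11.29%. With q = 0, every c is 0, the product collapses to S(360), and the estimate is exactly 10%.

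**Results by formula, m = 20%:**

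| True rate | None captured | Half captured | All captured |
|---|---|---|---|
| 10% | 10.0% | 10.65% | 11.3% |
| 20% | 20.0% | 21.2% | 22.3% |

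Simulation with 400,000 patients per scenario gives 9.9%, 10.6% and 11.3% for the first row and 20.1%, 21.3% and 22.2% for the second. A separate simulation gave 11.2% and 22.3% with all captured.

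**Sensitivity, all later events captured (simulated):**
- Every missed patient last seen on Day 270, m = 20%: 10.5% and 21.2%.
- Hazard concentrated early, m = 20%, mixed last visits: 10.9% and 21.6%.
- m = 5%: at most 10.3% and 20.5%.

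**Log-rank test with no true difference.** With 165 per arm and missed visits of 20% against 5%, the simulated type I error is 4.9 to 7.4% when all later events are captured and 4.6 to 5.9% when none are (simulation error about 0.4 points).

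**Why censoring everyone at Day 360 is not the repair.** If later events go uncaptured (m = 20%, mixed last visits), that rule gives 8.9% for a true 10% and 17.7% for a true 20%. A common cut-off for events and censoring is equivalent to q = 0 in the formula, and is unbiased when loss is unrelated to risk.

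**The case against.** A reader might infer that 5.5.2 contradicts 2.4.3. The text does not go that far. Section 2.4.3 offers Day 360 or end of study, and the protocol schedule labels Visit 9 as EOS. For patients with a Month 12 visit the two sections can be read as one rule. For the others, end of study could mean Day 360, a completion date or the last visit. That is an ambiguity to be resolved.

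A reader might also infer that stopping study drug by itself creates the long gap. Protocol 6.6.3, 6.6.6 and 6.6.8 require the Month 12 examination even after early discontinuation. The gap arises only for patients who also miss Visit 9.

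Nor do the documents support saying that one arm's rates are inflated or that a false safety signal follows. No missed-visit rate by arm is given. SAP 2.3.6 reports study discontinuations below 20% overall. That is not the same quantity as missed Month 12 visits, but it makes much larger scenarios hard to sustain.

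The best defence is that later events may hardly be captured. Protocol 6.6.6 treats patients who stop study drug and will clearly not return for Month 12 as withdrawn, and the glossary says no further assessments are planned after withdrawal. This stands in part: capture is probably incomplete, and with no capture the bias disappears. However, the graft-loss and death pages, and SAE reporting until 30 days after participation stops (Protocol 8.1), make zero capture unlikely.

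Finally, only the eGFR hypothesis is confirmatory (SAP 2.3.4), and power was not investigated for secondary endpoints. That limits the stakes but does not remove the asymmetry.

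**Conclusion.** The point holds in a conditional and modest form. Followed exactly, 5.5.2 makes follow-up depend on outcome for patients without a Month 12 visit, and 2.4.3 does not supply a clear rule in its place.

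With 20% lacking Month 12, loss unrelated to risk, constant hazard and mixed last visits, the upward bias on a true 10% is about 0.6 points if half of later events are captured and 1.2 to 1.3 points if all are. On a true 20% it reaches about 2.3 points. It is zero if none are captured. If higher-risk patients leave unseen, the net bias could be downward. A difference between arms needs a difference in missed visits, which remains an assumption.

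The figures do not cover the composite that counts loss to follow-up as an event, because some of these patients would then be events, and 5.5.2 gives no event date for that component. The primary analysis is untouched. The plan should be corrected, but nothing here undermines the trial's main conclusion.

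**What to change.** State one rule, in the same words, in SAP 2.4.3 and 5.5.2:

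- Define one cut-off date per patient without reference to whether an event occurred: the earlier of Day 360 and the last date to which status for that endpoint is ascertained. That date is the Month 12 visit, the Study Completion date, or the last contact at which rejection, graft and vital status were all assessed. Contact showing only that the patient is alive is not enough for the composite.
- Make clear that a patient still under follow-up when an event occurs has not yet reached a cut-off, so a death between scheduled visits still counts. The cut-off falls early only through withdrawal, loss or an early final visit, and a contact prompted by the event does not move it.
- Count only events on or before the cut-off, and censor event-free patients at it.
- Add a sensitivity analysis that includes events recorded after the cut-off, and report missing Month 12 visits by arm.

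The cost is SAP wording, one derived date and a few late events moved to the sensitivity analysis.
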